In recent years, artificial intelligence (AI) has developed methods to help us interpret *omics*. The analysis methods collectively known as *machine learning* or *deep learning* (DL), make it possible to consider the salient characteristics (*features*) and their constant variation throughout a population. In this way, algorithms can learn to classify new samples by recognising these characteristics (*features*) and evaluating them as a whole. These classification methods allow one transcriptomics to be distinguished from another one with a high degree of accuracy.

Previous evidence suggests changes in peripheral blood transcriptomics due to alterations predisposing to coronary heart disease. These changes are due to two main reasons. First, exposure to coronary risk factors (known and unknown) determines

changes in gene expression, particularly those related to metabolism, immunity, and platelet aggregation. Second, the development of coronary heart disease (and other complex diseases) is facilitated by predisposition represented by the inheritance of a significant number of variants in the genome. Thus, the trait of a complex disease can be predicted by measuring the polygenic risk score (PRS). Finally, recent studies confirm the association of heredity with exposure, thus combining the two dimensions in a single risk score.

In our preliminary tests, we worked on fine-tuning a measurement in a peripheral blood sample that allows the integration of all the genetics, including heredity as expression. We developed a novel way to analyze a biological sample's transcriptome through convolutional neural networks (*deep learning*). Our findings suggest that our analysis can classify the samples with very high precision. We applied this technology in a preliminary study, in which we found associations between surrogate points for cardiovascular disease and gene expression in peripheral blood. For example, we conducted a clinical study measuring coronary artery calcification (CAC), a clear surrogate marker of atherosclerotic disease and cardiovascular events, closely related to plaque load, of long-established prognostic value, and amenable to accurate noninvasive assessment by computed tomography (CT). In this study, we found clear indications of the clinical usefulness of our methodology.

The present clinical study proposes to identify atherosclerotic transcriptomic patterns from a whole blood sample. Likewise, as a secondary analysis, we will explore the ability of the algorithm to determine the presence of aortic disease and pro-inflammatory cardiometabolic alterations such as hepatic steatosis and surrogate markers of epicardial fat inflammation.

4. Background and Rationale

4.1. Cardiovascular disease

Cardiovascular disease (CVD) is the leading cause of death and disability globally. In 2019, CVD was responsible for approximately 18,600,000 deaths (32.8% of the total), and 80% occurred in low- and middle-income countries. (Mensah et al., 2019). It is possible that after the pandemic, these numbers have increased. The early detection of individuals at high risk of developing cardiovascular disease without symptoms has been and continues to be a challenge for science and health authorities worldwide. Implementing efficient and accessible methodologies for the detection of cardiovascular disease can lead to a radical change in the management of the disease, as well as a significant reduction in health spending associated with it and an extension in the population's life expectancy. The traditional approach to identifying individuals at increased risk of developing CVD or death from this cause is based mainly on the identification of single variables (diabetes, cholesterol, smoking), a group of variables ("Framingham Risk Score") or biomarkers (Hs-CRP, BNP, etc.) that are associated with a higher risk of developing this disease. Despite these advances, these approaches have a limited prediction capacity (Area under the curve 0.60-0.65) ([Y. Wang et al., 2019](#); [Rosenberg, 2010](#)). One possible cause of this limited effectiveness is that numerous processes (some known and many still unknown) are involved in developing chronic diseases that cannot be fully captured by analysing one or a few predictor variables. On the other hand, cardiovascular imaging is helpful for the early detection of CVD development (for example, carotid ultrasound and detection of CAC by CT). However, it requires expensive equipment and specialised personnel, so its use in clinical practice is scarce, and its implementation as a population screening tool is unlikely.

In recent years, the detection of genetic variants predisposing to coronary heart disease development has made significant progress. Like many other complex diseases, coronary heart disease has a hereditary component in its development. Classically, the

hereditary component was easily identifiable in two ways. Some patients develop symptoms at an early age (for example, a myocardial infarction under 45-50 years). Other patients have evident phenotypic traits (eg, familial hypercholesterolemia) that predispose them to cardiovascular events. These latter cases primarily respond to specific variants in the genome (monogenic diseases), but they are a minor part of the spectrum of patients with cardiovascular disease. Many patients with a genetic predisposition to cardiovascular disease inherit an extensive set of genomic variants. Although this polygenic inheritance is recognized, many genetic variants found concerning a phenotype do not have a clear causal relationship with the associated pathology. They are only associated with the phenotype because they are part of a haplotype and thus relate, either in *cis* or *trans*, to other causal variants. Coronary heart disease associated with specific haplotypes is becoming an effective method for cardiovascular prediction.

4.2. Transcriptomics

Cell DNA ensures that the biological information of a species is transmitted through generations. However, the interaction of DNA with the environment is established in different ways. The most direct and recognised is through the conversion of its code through the expression of RNA, a process known as transcription. The set of all expressed transcripts at a given time is known as the transcriptome. Therefore, it follows from these concepts that transcriptomics is the intersection of that information reserve that is DNA with modulation by signals from the ecosystem.

Within the structure of DNA are units known as *genes*. Until a few years ago, a gene was considered a DNA sequence that is transcribed into RNA and then translated into a protein. With this definition, it was found that the human genome contains approximately 22,000 genes, not very different from the number of genes that, for example, a fly contains (around 14,000) if we consider the phenotypic differences between one species and another. However, the definition of *gene* and the number have changed recently, possibly reaching as high as 100,000 (Salzberg, 2018). There are many sequences in DNA that are transcribed but not translated, known globally as

non-coding-RNA. These non-coding genes are the ones that mostly allow phenotypic differences between species, individuals, tissues and cells. Finally, the genes represented in the DNA sequence undergo significant changes after being transcribed, such as *splicing* or circularisation, which expands the possible number of differences between biological samples. In short, RNA represents the dynamic and active part of genetic information, profoundly modulated by the environment.

Technology has evolved to analyse the whole transcriptomics produced in a sample at a given time. This was partially done until a few years ago through a study known as a *microarray*, but it is currently done through massive RNA sequencing (RNA-Seq). In it, all the RNAs present at a given moment in a cell or tissue can be identified. However, the amount of information produced is enormous and must be ordered. For this, different *software* allows alignment with the human genome to identify each of the genes and count them to determine their expression level.

The development of massive sequencing and transcriptomics must also be seen in another context: lower costs. A few years ago, the cost per sample was well over a thousand dollars. However, the market launch of equipment with superior capabilities has markedly lowered the costs per sample. Therefore, this is a factor of paramount importance for developing clinical studies with tens or hundreds of patients. The next five years will see a continued expansion in reports of using RNA-Seq in patients. The determination of its clinical usefulness will depend on adequate analysis, for which the development of techniques based on artificial intelligence will facilitate its interpretation.

4.3. Polygenic risk score and its functional derivations

As previously mentioned, heredity plays a relevant role in some patients with coronary disease. In 2007, Samani et al. described the association of three haplotypes with early coronary disease (Samani et al.). Since then, multiple studies have shown the existence of specific haplotypes for different chronic diseases, including atherosclerosis and coronary heart disease (Musunuru and Kathiresan). These haplotypes have dozens of

genomic variants associated with a phenotype, each slightly associated with it. This minimal association is possibly the product of the absence of a direct causal relationship, and the existence of the minimal relationship is due to the absence of independent segregation of the alleles (*linkage disequilibrium*).

Based on the knowledge of the minimum association between variants and the possibility of massive DNA sequencing at low cost, population studies were carried out that allowed the development of risk scores for the development of complex diseases based on the sum of the minimum inherited risks. Thus, in recent years scores known as PRS (*Polygenic Risk Score*) have been designed, which result, for example, from the algebraic sum of the odds ratios of each of the variants. The higher the score, the higher the risk. This way of adding minimal risks proved efficient in discriminating against individual risks. Thus, a person in the highest risk decile has the same risk as a patient with familial hypercholesterolemia (Inouye et al., 2018; Klarin & Natarajan, 2021).

The clinical utility of the PRS is in the phase of clinical application, and it may be routine in the coming years. However, the PRS only measures the hereditary component of risk. Different researchers have proposed using PRS modified by including a component related to gene expression to establish a risk that also involves the environmental component of the risk, which may come from the association of genetic variants with epigenetic or transcriptome variations (Cano-Gamez & Trynka, 2020). In this way, the concept of *Transcriptome-wide Association Studies* (TWAS) was born, which measures risk based on the combination of inherited genetic variants and the expression of genes close to the same variants (Wainberg et al., 2017; Wainberg et al., 2019; Bhattacharya et al., 2020).

4.4. Evidence of alterations in peripheral blood in patients with atherosclerosis:

Atherosclerosis is known as a vascular disease caused by the deposition of cholesterol in inflammatory cells in the middle layer of the arteries. The consequences of

these deposits are well known: exposure to lipid-containing inflammatory cells after plaque rupture produces most of the acute intravascular thrombotic events, including myocardial infarction, some types of stroke, and peripheral arterial disease. (Wolf & Ley, 2019; Geovanini & Libby, 2018). Non-occlusive events eventually lead to low blood flow ischemia.

From the preceding, the necessary interaction between inflammatory cells, metabolism and the vascular wall in the pathophysiology of atherosclerotic disease is deduced. This complex interaction is often measured in clinical practice by surrogate biomarkers of vascular status and the odds of unfavourable outcomes of atherosclerotic disease. These markers can be representative of metabolic changes (cholesterol, blood glucose, free fatty acids, etc.), inflammatory (C-reactive protein, interleukins, leptin, etc.) or coagulation (fibrinogen, PAI-1, etc.). Furthermore, many still unknown markers are present in peripheral blood, originating from new cardiovascular risk factors described in recent years, such as the intestinal microbiome (Barrington & Lusic, 2017; Komaroff, 2018) or air pollution (Jilani et al., 2020). In addition, these markers can be of different molecular types: protein, RNAs of various shapes, or even small molecules.

Among the possible biomarkers mentioned in the previous paragraph are RNA molecules. Blood cells are subjected to all kinds of signals from the tissues they perfuse. These signals impact circulating cells, or even progenitors in the bone marrow, thereby modifying gene expression. Thus, the different states of a disease can present a set of differentially expressed genes. Various studies have confirmed the existence of genes expressed in patients with atherosclerotic disease. Alterations in gene expression in blood cells are evidenced in different states of predisposition to atherosclerosis (Ding et al., 2015), prognostic evolution (Holvoet et al., 2016), or response to treatment with statins (Kini et al., 2017). Furthermore, the expression of a set of genes has been associated with clinical variables to predict the severity of atherosclerotic disease (Y. Wang et al., 2019). Therefore, these studies show the existence of alterations in gene expression in patients with cardiovascular disease. It is currently claimed that these changes can be used in the

future as markers of the disease and its evolution (Marín de Evsikova et al., 2019; Chen & Stewart, 2016; Friede et al., 2015; Rhees & Wingrove, 2015).

4.5. Artificial intelligence

Artificial intelligence (AI) has spread widely in recent years thanks to the development of new algorithms that allow enormous growth in classification capabilities. The possible applications of this in many areas of human activity have led to AI being considered a new milestone in the evolution of humanity. In particular, for medicine, it can mean a stage of enormous changes in how it is practised (Topol, 2019).

AI can be defined as a set of algorithms and equations that can mimic certain cognitive behaviours of human beings. While the term suggests reasoning capabilities, AI is currently only limited to a human (or even super-human) ability to interpret and classify big data. For this purpose, mathematical algorithms are used, collectively known as *machine learning*. One, in particular, has stood out for some years, known as the neural network. This algorithm involves many parallel and serial linear equations, each modified by one or more nonlinear equations, forming a network of equations, ending in a nonlinear equation that determines a probability. The latter is used for probabilistic classification. Although this algorithm has been known for decades, specific changes in recent years have allowed its enormous expansion, leading them to be known as *deep learning* (LeCun et al., 2015). These changes are mainly of two types: first, the ability for the network to correct itself was developed in the 1980s by employing an algorithm called *backpropagation* (Rumelhart et al., 1986); Drucker & Le Cun, 1992). This algorithm allows the neural network to adjust in successive cycles to modifications that progressively improve its predictive capacity (*training*) in successive cycles. The second reason for the expansion of *deep learning* corresponds to the development of *hardware* that makes it possible to carry out a large number of simple calculations (linear regressions) in a short time, mainly through the adaptation of “GPUs” (*Graphical Processing Units*) for use in AI. From these two advances, the science of *deep learning* has expanded remarkably, with increasing participation in processes of daily life.

4.6. Use of artificial intelligence in medicine

Many examples have emerged in recent years about the potential of AI in medicine. One of the most important studies was published in 2017, in which an algorithm was fed photographs of skin lesions, including different forms of skin cancer. The algorithm was able to differentiate those malignant lesions with higher accuracy than a group of dermatologists (Esteva et al., 2017). Another study of equal importance demonstrated a high capacity of DL to distinguish the presence of tumour cells in histopathological images of axillary lymph nodes of patients with breast cancer (Ehteshami Bejnordi et al., 2017). These two examples are a sample of the impact of advances in development in this area: a trained algorithm can automatically distinguish alterations present in an image, regardless of the doctor. The enormous potential for diagnostic help of these algorithms is an impetus for research on them.

Although the use of AI in medicine is in its infancy and the research stage, possible applications of AI in medicine can be grouped into the following spaces:

- Radiology: AI algorithms can be fed with imaging studies, and they can learn characteristics associated with abnormal defects. Based on these capabilities, there is a growing number of potential AI applications in this field, and some of them have already been approved for clinical use. Soon, many of the most common images in radiology will be previously scanned by an algorithm to preliminarily identify if there is an alteration, alleviating the work of the doctor who will only focus on those that contain a pathological alteration. Various studies have shown the usefulness of DL in multiple areas of the cardiovascular field, from a risk stratification and triage tool to the automatic evaluation of ventricular volumes in magnetic resonance imaging and the coronary calcium score by CT.
- Body images: Successful examples in this area are also expected due to DL's good results in image processing. For example, the interpretation of skin lesions is feasible with DL. Another example is the analysis of fundus images, possibly predicting cardiovascular risk. But in addition, neural networks can recognise

whether an eye fundus image is of a man or a woman with an accuracy of approximately 98%, which speaks to their ability to extract imperceptible features from an image. It is not known precisely what characteristics define the differences in the images, but they may be related to the thickness of the arteries or another variation imperceptible to the human eye (Poplin et al., 2018; Nent et al., 2019).

- Continuous signals: This is the case of the use of AI for interpreting data coming from continuous acquisition signals. Examples of them are, for example, the interpretation of an electrocardiogram or electroencephalogram by a DL algorithm (Hannun et al., 2019; Craik et al., 2019).
- Language processing: The interpretation of language is being revolutionised by DL. The automated analysis of medical records or the patient vocabulary are examples of how it can be applied. There are multiple reports where they identify emotions, including depressive states, from the language used by a subject (Liang et al., 2016).

5. Preliminary observations

5.1. In silico developments

In our laboratory, we have developed a methodology for transcriptome analysis based on extensive bioinformatic processing of a biological sample and its subsequent interpretation employing a *deep learning algorithm*. In this way, we can incorporate all the genes read in a sequence and perform a classification using a supervised method. This algorithm has proven robust and highly accurate in our preliminary tests. The development comprises a *pipeline* that takes the RNA-seq sample in its crudest state and analyses it entirely, including coding and non-coding RNAs, circular RNAs and the blood microbiome. The algorithm is trained with all the samples of a cohort, previously classified, and later, the algorithm is validated with 10 or 20% of the samples.

The analysis of the efficiency of the algorithm was performed with different RNA-seq databases available in digital repositories. First, we used the GTEx database, which has taken *postmortem* from dozens of people and performed sequencing of them. In total, 30 different tissues containing 11,866 sequences were analyzed. The analysis of our algorithm achieved a correct prediction in 99.1% of the cases (figure 1). The few errors correspond to potentially similar tissues (for example, breast with fatty tissue).

Subsequently, we analyzed the Genomic Data Commons (GDC) database, which has RNA sequencing of biopsies from different tumors. We analyzed 10,000 biopsies distributed in 34 tumors. Again, the predictive capacity of the algorithm was very high, reaching 97.5% (figure 2). These two analyses show that the algorithm has a great classification capacity between multiple samples.

We then performed a sensitivity analysis of the algorithm. To do this, we started with 100 random samples taken from brain tumors from the GDC database, 50 of them corresponding to GBM and 50 of them to GL. With them, new training was carried out in which we achieved a precision of 100%, which translates into an area under the curve (ROC) of 1. Successively, we removed samples at random, performing effective training with only 30 samples (15 of each group). Therefore, the algorithm has a very efficient behaviour with a low number of clinical cases. This reflects the fundamental differences in gene expression between the two groups of tumors.

the analysis capacity of neural networks makes it possible to consider this great mass of information with an unprecedented capacity to interpret this data. These findings then lead us to propose the hypothesis that our pipeline may be useful in detecting tumour pathologies in peripheral blood transcriptomics.

5.2. Preliminary studies

We previously developed a clinical protocol with the aim of perfecting the methodology that will be used in this study. The initial goal was to develop blood collection, RNA isolation, library generation for sequencing, and RNA sequencing. Briefly, the preliminary results of these steps, performed on 540 samples from 3 different studies, are described below.

First, a robust methodology was established to obtain an RNA sample from peripheral whole blood (without cell separation). Samples were collected in PaxGene RNA tubes through antecubital vein puncture. No adverse effects were observed in this procedure. Samples were stored at -20°C until RNA extraction. This step was performed through the use of a specific kit (Thermo-Fischer). As a result, it was possible to consistently obtain RNA samples in sufficient quantities for sequencing in all cases. Then, the library was built, a process in which the RNA is transformed into cDNA (complementary DNA), from which the RNA corresponding to ribosomes and globin are extracted, fragmented, and finally the adapters are added at the ends. Again, the library construction was developed in a robust way for all the analyzed samples.

Subsequently, RNA sequencing was performed at a depth of 100 million reads. Between 20 and 25 thousand genes expressed in peripheral blood were detected in all the samples (n=540). In a series of patients, computed tomography was performed to determine the degree of calcification of the coronary arteries (Coronary Calcium Score, CCS). An analysis of gene expression in peripheral blood was performed and genes related to the degree of coronary calcification were found.

[figure not shown]

Figure 3: Preliminary results. We analyzed 38 samples from patients who had coronary calcium measured. The left panel shows the result of a PCA analysis where a moderate but significant reduction in dimensionality is found based on the extent of coronary calcium. The heatmap shows the differentially expressed genes between the two groups.

6. Study Objectives

Primary Objective

The primary objective of the study is to evaluate the diagnostic accuracy of peripheral whole blood transcriptomes analyzed by an artificial intelligence algorithm to detect the presence and extent of coronary calcification in individuals without a history of known cardiovascular disease.

Specific Primary Objectives

1. To classify transcriptomes according to the presence and extent of coronary calcification by noncontrast cardiac CT.
2. Train artificial intelligence algorithms with information from the transcriptome to recognize the presence and extent of calcification in coronary arteries.

-
3. To determine the degree of diagnostic accuracy of the method to detect the presence and extent of coronary calcification non-invasively.

Secondary objectives

1. To determine the degree of diagnostic accuracy of the method to detect the presence and extent of:
 - Aortic
 - calcification Aortic valve calcification
 - Hepatic steatosis
 - Volume of epicardial fat
 - Volume of high-density epicardial fat (upper quartile)
 - Enlargement of cardiac cavities To
2. To explore differences in transcriptomics of peripheral blood between patients who did and did not develop a CV event during follow-up.
3. To explore different electrocardiographic patterns according to the results of cardiac CT and peripheral blood transcriptomics.
4. Generate a polygenic risk score (PRS) from the transcriptome and/or exome sequencing and associate it with the transcriptome and coronary calcification.

7. Methods

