8.5. Analysis of cardiac CT

The presence of CAC and its extension will be evaluated using both ordinal variables (number of segments with CAC and number of affected vessels, and qualitatively: absence, mild, moderate, and severe; and the number of coronary segments with calcification) as continuous variables (Agatston units). The presence and extension of calcifications at the level of the aortic valve and the thoracic aorta (Agatston units) will also be evaluated independently. The extent of aortic calcification will be evaluated in sections that include from the bifurcation of the pulmonary artery as the upper limit to the diaphragm as the lower limit.

Quantitative analysis of SCC will be performed using dedicated software (HeartBeat-CS, Philips Healthcare, Best, The Netherlands). Finally, the volume and density of epicardial fat will be calculated by evaluating the volume of tissue with a density between -190 and -30 HU located in the area between the epicardium and the pericardium, the bifurcation of the pulmonary artery as the upper limit, and the diaphragm as lower limit.

Finally, the density of the hepatic parenchyma will be calculated through a region of interest >100 mm² at the level of the right and splenic lobes. From these measurements, the presence of hepatic steatosis will be defined from a quotient of less than 1.

At least 20% of the participants (randomly selected) will have a double reading of the main outcome of the study (presence or extent of CACs). This reading will be carried out by an expert external to the group of researchers of the study and blind to the first reading. In case of disagreement, consensus will be sought between the two experts. The aim of this process is to enhance the internal validity of the study.

The epicardial fat volume analysis will be performed by experts from the University of Palermo (Italy).

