9.4. Analysis plan

For the description of the general characteristics of the study population, descriptive statistics such as means, medians and proportions will be used. To calculate the diagnostic performance of the method, the following will be calculated:

- True Positives (TP) or the probability that the test is positive since the disease is present

-
- True Negatives (TN) or the probability that the test is negative since the disease is not present.
 - False Positives (FP) or Type I Error
 - False Negatives (FN) or Type II Error
 - Sensitivity: $VP/VP+FN$
 - Specificity: $VN/ VN+FP$
 - Precision or accuracy: $VP/VP+FP$ or sensitivity + (1-specificity)

The diagnostic precision can vary between 0.5 and 1, where 1 represents a perfect diagnostic value and 0.5 is a test without diagnostic discriminatory capacity. An area under the curve (AUC) will also be performed to determine the diagnostic capacity of the trained algorithm.

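### Total epicardial fat volume is a diagnostic-accuracy target in secondary objective 1, but the plan gives neither a cut-off for it nor any measure for a continuous outcome

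*Combined protocol and SAP*

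**What the plan says.** - **Section 6, Secondary objectives, item 1.** The task is "To determine the degree of diagnostic accuracy of the method to detect the presence and extent of" a list of CT findings. One bullet is "Volume of epicardial fat", with no threshold or percentile. The bullet after it, "Volume of high-density epicardial fat (upper quartile", does carry a percentile label, but that label belongs to high-density fat and not to total volume.
- **Section 8.5.** It states that "the volume and density of epicardial fat will be calculated by evaluating the volume of tissue with a density between -190 and -30 HU". The attenuation window decides which tissue is counted. It does not divide participants into affected and unaffected. For a different secondary target the same section does give a rule: "the presence of hepatic steatosis will be defined from a quotient of less than 1".
- **Section 9.4.** The diagnostic measures are the four cells of a 2x2 table, sensitivity, specificity, precision or accuracy, and an AUC. The negative class is described as "the probability that the test is negative since the disease is not present". No measure for a continuous target is listed.
- **Section 9.3.** The sample size is 800. It is not derived for this target, and no alpha, power or effect size is stated.

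**The concern.** The objective, the measurement and the analysis do not fit together for this item. The CT reading produces a number for each participant, while every measure in section 9.4 needs each participant classed as having or not having the condition. Nothing in the documents links the two. The extent half of the objective does not help, because section 9.4 has no measure of how well a continuous quantity is predicted.

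Two things are at stake. An analyst who follows section 9.4 must supply a cut that the plan does not state, and nothing in the plan prevents that choice from being made once volumes and predictions are both known. Also, any cut reduces a measured volume to two classes, so a modest but real association between the blood transcriptome and epicardial fat is harder to show and less precisely described.

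**Working it through.** **1. Can the section 9.4 measures be computed on the item as written?**

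Without a cut, the only literal meaning of presence is a volume above zero. Assume, since the documents do not say so, that every participant has some measurable epicardial fat. Then all 800 are positive and 0 are negative. Specificity = TN/(TN + FP) = 0/0, and the number of positive-negative pairs for the AUC is 800 x 0 = 0. Neither measure is defined. This is unlikely to be what the sponsor means, so some cut must be intended or later supplied.

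**2. Does the choice of cut matter?**

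Illustration with 160 validation participants. This is 20% of 800, a share borrowed from the in silico work in section 5.1 and not set for this study. Assume a true AUC of 0.75 and use the Hanley-McNeil variance:

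var = [A(1-A) + (n1-1)(Q1-A²) + (n0-1)(Q2-A²)]/(n1 n0), with Q1 = A/(2-A) = 0.600 and Q2 = 2A²/(1+A) = 0.643.

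- Upper quartile, 40 positive and 120 negative: var = (0.1875 + 39 x 0.0375 + 119 x 0.0804)/4800 = 0.00234, so the 95% half-width is 1.96 x 0.0483 = 0.095.
- Median, 80 and 80: var = (0.1875 + 79 x 0.0375 + 79 x 0.0804)/6400 = 0.00148, so the half-width is 1.96 x 0.0385 = 0.076.

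Once a cut is named, the measures exist. Class sizes and precision depend on which one it is.

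**3. What does a cut discard?**

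For a normally distributed outcome with a fraction q above the cut, the retained efficiency is φ(z)²/[q(1-q)], where φ is the standard normal density at the cut z.

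- Median (q = 0.50, z = 0): 0.3989²/0.25 = 0.637. The loss is 36%, and 800 participants carry the information of 800 x 0.637 = 509.
- Upper quartile (q = 0.25, z = 0.674): 0.3178²/0.1875 = 0.539. The loss is 46%, and 800 carry the information of 431.

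**4. What does that mean for power?**

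The plan states no test for this item, so this is illustration only. Assumptions: bivariate normal predicted and measured volumes with true correlation r, and a two-sided 5% level. The continuous analysis is a Pearson test; after a split it is a Mann-Whitney test. Power is simulated and good to about 0.02.

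| Validation n | r | Continuous | Median split | Upper-quartile split |
|---|---|---|---|---|
| 160 | 0.15 | 0.47 | 0.29 | 0.27 |
| 160 | 0.20 | 0.73 | 0.51 | 0.44 |
| 160 | 0.25 | 0.90 | 0.70 | 0.62 |
| 160 | 0.40 | 1.00 | 0.98 | 0.96 |
| 80 | 0.25 | 0.60 | 0.40 | 0.34 |

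The continuous analysis is ahead in every row. At n = 160 the gap is about 20 to 30 points for r from 0.15 to 0.25, and at most 4 points at r = 0.40.

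**The case against.** The strongest reply is that this is an omission and not an unworkable endpoint. A reader might infer that a volume has no disease-absent state, so that the endpoint cannot be evaluated at all. The documents do not support that. The objective covers extent as well as presence, a volume can be dichotomised, and step 2 shows that specificity and AUC follow once a cut is named.

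A reader might also infer that a cut invented after the fact is the only route, or that a favourable cut will be picked. That does not follow either. A percentile rule could be added in one line now. Even a cut set after the CT reading need not be informed by results: section 7.1 places sequencing at the end of enrolment, and section 8.5 sends the epicardial fat analysis to an outside university group. A cut could therefore be fixed before any prediction exists. What stands is that the plan does not commit to this.

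It is also fair to say that the power figures rest on an assumed correlation and a borrowed validation share, and that a binary target suits the classifier described in section 8.4. For that reason the figures are given as a range, and the finding does not depend on them.

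Finally, the gap is wider than this bullet. Enlargement of cardiac cavities has no definition in section 8.5, and section 9.4 has no extent measure even for coronary calcification. That is a reason to repair section 9.4 more generally. It does not remove the point here, where a continuous CT measurement is already planned and a better analysis is at hand.

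**Conclusion.** The point holds in this form: the plan specifies neither a cut-off nor a continuous measure for total epicardial fat volume, so neither its presence nor its extent can be analysed under section 9.4 without a choice that the plan leaves open. That follows from sections 6, 8.5 and 9.4 read together and needs no numerical assumption.

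The cost of imposing a cut is about 36% of efficiency at the median and 46% at the upper quartile, if volume is roughly normal. The power consequence cannot be fixed from the documents. It is substantial if the true correlation is weak and close to nil by about r = 0.40 with 160 validation participants.

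The stakes are limited. This is one bullet of a secondary objective, and the introductory text just before section 4 describes the secondary analysis as exploratory. The primary objective is unaffected. The change should be made, but the study's main conclusion does not depend on it.

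**What to change.** 1. In section 6, take total epicardial fat volume out of the presence-and-extent list and state it as predicting epicardial fat volume in mL.
2. In section 9.4, add for this endpoint a network output trained on the continuous volume. In participants not used for training, report the correlation or R-squared between predicted and measured volume, the calibration slope and the mean absolute error, each with a 95% CI.
3. If sensitivity, specificity or AUC are also wanted, report them only as a supplement, at a cut or percentile rule written into the plan before any predictions are available.

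The cost is wording in two sections, one extra regression output and slightly more analysis work. The volumes are already to be measured, so no further participants, scans or sequencing are needed.
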